2.4 Other endpoints

- At least one treatment-emergent systemic allergic reaction including anaphylaxis¹⁷
- At least one TEAE treated with adrenaline/epinephrine
- At least one treatment-emergent severe local swelling or oedema of the mouth and/or throat
- A TEAE of eosinophilic oesophagitis
- A TEAE leading to discontinuation
- Daily duration of recurrent TEAEs

¹⁷ The definition of anaphylaxis according to (Sampson et al. 2006), see section 12

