11.16 Solicited signs/symptoms

In order to aid the AE and concomitant medication reporting, subjects will be given a paper diary to fill in daily (See Appendix 4). The diary will be used by the subject to help remember details and dates, when discussing AEs and concomitant medication with the investigator at the telephone contact and at visit 3 (and unscheduled visits, if applicable).

The diary will be used to capture 15 pre-specified symptoms/signs, identified as potential local side effects of sublingual immunotherapy (Passalacqua et al. 2013):

- Food tastes different
- Mouth ulcer/sore in the mouth³⁰

³⁰ A mouth ulcer is a discrete, painful lesion affecting the lining of the mouth where the mucosa is eroded

- Swelling of uvula/back of the mouth
- Itching in the mouth
- Itching in the ear
- Swelling of the lips
- Swelling of the tongue
- Tongue pain
- Tongue ulcer/sore on the tongue³¹
- Throat irritation/tickle
- Throat swelling
- Stomach pain
- Nausea (feel like throwing up)
- Vomiting
- Diarrhoea

If the subject answers “yes” to any of the symptoms, listed in the diary, the subject must also fill in whether any medication was used to treat this symptom and what type of medication.

Subjects and their legal representative will be trained by the investigator or designee at V2 on the proper method to complete the diary. In addition, the subject will be instructed to report other symptoms, that are not part of the diary list, to the investigator. The reported symptoms will be discussed with the subjects and after medical evaluation by the investigator be reported as AEs on the AE form in the eCRF. The evaluation of the solicited signs/symptoms must be documented in the medical records.

When evaluating the diary together with the subject at V3 the investigator should identify use of medication reported on the diary and fill each use of medication into the eCRF linked to the relevant AE.

If any AEs are reported on several consecutive days, the investigator should mark the AE as “recurrent” and inquire about the approximate duration each day of these recurring AEs and enter this information into the eCRF (see section 12.3).

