12.1 Definitions

12.1.1 Adverse events

An AE is any untoward medical occurrence in a clinical trial subject, and which does not necessarily have a causal relationship with the administered IMP.

An AE can therefore be any unfavourable and unintended sign (including e.g. a medication error), symptom, or disease, whether or not considered related to the IMP.

The following events should not be recorded as AEs:

- A pre-planned procedure, e.g. a surgical intervention, unless the condition for which the procedure was planned has worsened since the informed consent form was signed.
- Pre-existing conditions documented as medical history. However, any worsening in severity or frequency of a pre-existing condition during the clinical trial period must be regarded as an AE.

Events of special interest

Selected AEs will be considered events of special interest (ESIs). ESIs are events that are considered critical for the evaluation of the product's safety profile and for which additional data will be collected. ESIs for this trial are:

- Systemic allergic reactions including anaphylaxis³²
- Events treated with adrenaline/epinephrine
- Severe local swelling of the mouth and/or throat
- Eosinophilic oesophagitis

See Appendix 5 for definitions and aggregated preferred terms used to identify ESIs.

³² The definition of anaphylaxis (Sampson et al. 2006) includes any 1 of the following 3 criteria:

1. Acute onset of an illness (minutes to several hours) with involvement of the skin, mucosal tissue, or both (e.g., generalised hives, pruritis, or flushing, or swollen lips, tongue, or uvula) AND either respiratory compromise (e.g., dyspnoea, wheeze-bronchospasm, stridor, reduced PEF, hypoxemia) or reduced BP* or associated symptoms of end-organ dysfunction (e.g., hypotonia [collapse], syncope, incontinence)
2. Two or more of the following that occur rapidly after exposure to a likely allergen for the subject (minutes to several hours):
 - a. Involvement of the skin-mucosal tissue (e.g., generalised hives, itch-flush, swollen lips, tongue, or uvula)
 - b. Respiratory compromise (e.g., dyspnoea, wheeze-bronchospasm, stridor, reduced PEF, hypoxemia)
 - c. Reduced BP* or associated symptoms (e.g., hypotonia [collapse], syncope, incontinence)
 - d. Persistent gastrointestinal symptoms (e.g., crampy abdominal pain, vomiting)
3. Reduced BP after exposure to known allergen for the subject (minutes to several hours): low systolic BP* or greater than 30% decrease in systolic BP

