12.3.3 Reporting of AEs

The investigator must report all SAE and ESI information (initial as well as follow-up) to ALK within 24 hours after obtaining knowledge of the information. SAEs and ESIs will automatically be sent to ALK via the eCRF system. In case the eCRF system is unavailable during the 24-hour reporting timeline, SAEs and ESIs (including relevant data e.g. demography, medical history, concomitant medication) must be reported by email to ALK. For the ESI of adrenaline/epinephrine administration, the symptoms and/or circumstances that triggered the use of adrenaline/epinephrine must be clearly recorded as AEs in the eCRF.

Non-serious AEs should be reported within 5 working days after obtaining knowledge of the information.

If requested, please forward supporting documents to ALK via email. Please state the trial ID (MT-18) and the site and subject ID on all documents.

IMPORTANT: Any information that could reveal the identity of the trial subject must be hidden or removed in the source documentation. Also, information that is not relevant for the subject and the subject's condition must be hidden or removed.

Email address: [contact]

Emergency [contact]

The assessment of listedness is performed by ALK according to the reference safety information in the current version of the approved IB.

ALK will inform the regulatory authorities and IECs in accordance with local requirements in force and the ICH guidelines for Good Clinical Practice (GCP) (ICH 1996).

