15.8.1 Evaluation of AEs

Below is the list of the safety endpoints in the trial:

Primary endpoint	At least one TEAE
Secondary endpoint	At least one solicited TEAE
Secondary endpoint	At least one IMP-related AE
Secondary endpoint	At least one treatment-emergent serious adverse events (SAE)
Other	At least one treatment-emergent systemic allergic reaction including anaphylaxis
Other	At least one TEAE treated with adrenaline/epinephrine
Other	At least one treatment-emergent severe local swelling or oedema of the mouth and/or throat
Other	A TEAE of eosinophilic oesophagitis
Other	A TEAE leading to discontinuation
Other	Daily duration of recurrent TEAEs

The different types of AEs (TEAEs, solicited TEAEs, IMP-related AEs, treatment-emergent SAEs, treatment-emergent systemic allergic reactions including anaphylaxis, TEAEs treated with adrenaline/epinephrine, treatment-emergent severe local swellings or oedemas of the mouth and/or throat, TEAEs of eosinophilic oesophagitis, and TEAE leading to discontinuation) in the above table will be summarised by system organ class (SOC) and preferred term (PT).

Summaries will include number and proportion of subjects having the event, as well as number of events. For the proportion of subjects with at least one events the exact 95% confidence interval will also be presented.

The different types of AEs mentioned in the above table will generally also be summarised according to severity, relationship to trial product, outcome, action taken, seriousness, and number of events leading to treatment discontinuation. However, in case of few events of the specific type, these details will be listed instead.

Duration of recurrent TEAEs will be summarised according to PT.

Most frequent AEs defined as those occurring in more than 2% of subjects will be summarised according to SOC and PT. Duration of most frequent AEs, as well as time to onset of most frequent AEs, will be summarised according to SOC and PT.

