Appendix 5**
**Preferred terms for solicited AEs and preferred terms in
aggregated terms**

Trial ID: MT-18

Investigational Medicinal Product: HDM SLIT-tablet

Phase: IV

EudraCT No.: 2020-000446-34

Sponsor: Global Clinical Development
ALK-Abelló A/S
[name]
[contact]

Document Status: Final

Date: 06-Feb-2020

Version: 1.0

Confidential

Property of ALK

May not be used, divulged, published or otherwise disclosed without the written consent of
ALK

Table of Contents

1	Solicited signs/symptoms.....	3
2	Systemic allergic reactions including anaphylactic reactions	4
3	Local swelling or oedema of the mouth and/or throat.....	8
4	Medication errors	9
5	Drug abuse, misuse and overdose	14

1 Solicited signs/symptoms

Preferred terms (PTs) representing the solicited signs/symptoms have been selected (MedDRA 22.1, PTs will be updated to current MedDRA version at the time of reporting). All AEs with these PTs occurring during the 28 days treatment period will be defined as solicited AEs.

Solicited signs/symptoms patient card term	Solicited AE PT
Food taste different	Dysgeusia
Mouth ulcer/sore in the mouth	Mouth ulceration
Swelling of the uvula/back of the mouth	Enlarged uvula Oedema uvula Palatal swelling Palatal oedema Mouth swelling Oedema mouth
Itching of the mouth	Oral pruritus
Itching in the ear	Ear pruritus
Swelling of the lips	Lip swelling Lip oedema
Swelling of the tongue	Swollen tongue Tongue oedema
Tongue pain	Glossodynia
Tongue ulcer/sore on the tongue	Tongue ulceration
Throat irritation/tickle	Throat irritation
Throat swelling	Pharyngeal edema Pharyngeal swelling
Stomach pain	Abdominal pain upper Abdominal pain
Nausea (feel like throwing up)	Nausea
Vomiting	Vomiting
Diarrhea	Diarrhea

2 Systemic allergic reactions including anaphylactic reactions

Cases of possible systemic allergic reaction and/or anaphylaxis are identified by using the following criteria (MedDRA version 22.1, PTs will be updated to current MedDRA version at the time of reporting):

Standardised MedDRA Query (SMQ):

- Anaphylactic reaction, including algorithm:
 - A narrow term from category A;
 - A term from category B – (upper airway/respiratory) AND a term from category C – (angioedema/urticaria/pruritus/flush). Events co-occurring within 24 hours.
 - A term from category D – (cardiovascular/hypotension) AND a term from category B – (upper airway/respiratory) OR a term from category C (angioedema/urticaria/pruritus/flush). Events co-occurring within 24 hours.

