3 Local swelling or oedema of the mouth and/or throat

Preferred terms (PTs) indicating swelling or oedema in the mouth and/or throat have been selected (MedDRA 22.1, PTs will be updated to current MedDRA version at the time of reporting). AEs with these PTs will be used for summary of the ESI local swelling or oedema if the mouth and/or throat.

PTs for identification of laryngo-pharyngeal swellings/oedemas
Dysphagia
Dysphonia
Epiglottic oedema
Laryngeal dyspnoea
Laryngeal obstruction
Laryngeal oedema
Laryngotracheal oedema
Mouth swelling
Oedema mouth
Oropharyngeal swelling
Oropharyngeal oedema
Palatal oedema
Palatal swelling
Pharyngeal oedema
Pharyngeal swelling
Sensation of foreign body
Suffocation feeling
Swollen tongue
Throat tightness
Tongue oedema
Tracheal oedema

4 Medication errors

Preferred terms (PTs) related to medication errors have been selected by using the following criteria (MedDRA version 22.1, PTs will be updated to current MedDRA version at the time of reporting):

Standardised MedDRA Query (SMQ):

- Medication errors

PTs for identification of medication errors
Accidental device ingestion
Accidental device ingestion
Accidental device ingestion by a child
Accidental exposure to product
Accidental exposure to product by child
Accidental exposure to product packaging
Accidental exposure to product packaging by child
Accidental overdose
Accidental poisoning
Accidental underdose
Accidental use of placebo
Booster dose missed
Circumstance or information capable of leading to device use error
Circumstance or information capable of leading to medication error
Contraindicated device used
Contraindicated product administered
Contraindicated product prescribed
Deprescribing error
Device dispensing error
Device monitoring procedure not performed
Device programming error
Device use confusion
Device use error
Dietary supplement prescribing error
Discontinued product administered
Documented hypersensitivity to administered product
Dose calculation error
Drug administered in wrong device
Drug dispensed to wrong patient
Drug dose omission by device
Drug dose titration not performed
Drug monitoring procedure incorrectly performed

PTs for identification of medication errors
Drug monitoring procedure not performed
Drug titration error
Duplicate therapy error
Expired device used
Expired product administered
Exposure via direct contact
Exposure via eye contact
Exposure via skin contact
Extra dose administered

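### The Appendix 5 term list for the local swelling event of special interest omits Enlarged uvula and Oedema uvula, so a severe uvula swelling coded to either term is not selected for that endpoint

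*Combined protocol and SAP*

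**What the plan says.** The endpoint in section 2.4 is "At least one treatment-emergent severe local swelling or oedema of the mouth and/or throat"; it is listed again in section 15.8.1. Section 12.1.1 names severe local swelling of this kind as an event of special interest (ESI) and sends the reader to the appendix: "See Appendix 5 for definitions and aggregated preferred terms used to identify ESIs".

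Appendix 5, section 3 gives the list for this ESI. Its scope is stated as "Preferred terms (PTs) indicating swelling or oedema in the mouth and/or throat have been selected", and its use as "AEs with these PTs will be used for summary of the ESI local swelling or oedema if the mouth and/or throat". The list has 21 PTs and contains neither Enlarged uvula nor Oedema uvula.

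The uvula is nevertheless part of what the trial solicits. Section 11.16 has the diary item "Swelling of uvula/back of the mouth", and Appendix 5, section 1 maps that item to "Enlarged uvula Oedema uvula Palatal swelling Palatal oedema Mouth swelling Oedema mouth".

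**The concern.** The two lists are in one appendix, cite the same dictionary version (MedDRA 22.1) and cover overlapping anatomy. Section 1 treats the uvula as part of the back of the mouth. Section 3 claims to cover the mouth and throat, yet it takes four of the six PTs for that diary item and drops the two that name the uvula.

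The section 3 list is the stated rule for selecting events. A severe treatment-emergent uvula swelling coded to either missing PT would therefore satisfy the endpoint as worded but not be picked up when it is counted. The sample-size argument in section 15.1 names severe local swelling as one of its two rare event types and reasons from a single event, so one lost case would matter to how the result reads.

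**Working it through.** **Comparison of the lists.** Inputs are the solicited swelling PTs in Appendix 5, section 1, the ESI list in section 3, and the systemic reaction list in section 2. The spelling Pharyngeal edema in section 1 is matched to Pharyngeal oedema in section 3.

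| Solicited swelling item | PTs in section 1 | On section 3 list | Missing from section 3 | Missing PTs found in section 2? |
|---|---|---|---|---|
| Uvula/back of mouth | 6 | 4 | Enlarged uvula, Oedema uvula | No |
| Tongue | 2 | 2 | none | – |
| Throat | 2 | 2 | none | – |
| Lips | 2 | 0 | Lip swelling, Lip oedema | Yes, category C |
| Total | 12 | 8 | 4 | |

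The section 3 list runs essentially in alphabetical order from Dysphagia to Tracheal oedema. Neither uvula term stands where it would belong (before Epiglottic oedema, and after Oedema mouth), so a broken table does not explain the gap. The lip terms raise a separate scope question. Only the uvula terms are absent from both ESI term lists.

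**The plan's own figure.** Section 15.1 gives 0.95% as the upper limit of a two-sided 90% interval for 1 event in about 500 pooled adolescents. The exact (Clopper-Pearson) upper limit for x events in n subjects is the 1 − α/2 quantile of a Beta(x + 1, n − x) distribution. With x = 1, n = 500 and α = 0.10 it is 0.945%, which agrees. With n = 265 + 250 = 515 it is 0.92%.

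**Illustration in this trial.** Section 15.8.1 plans exact 95% intervals, so α = 0.05. For x = 0 the upper limit reduces to 1 − 0.025^(1/n); at n = 250 this is 1.465%. For x = 1 and n = 250 the interval is 0.010% to 2.208%. Enrolment is only approximately 250, so 225 and 275 are assumed here as a range.

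| n | Upper limit, 1 event counted | Upper limit, that event missed (0 counted) |
|---|---|---|
| 225 | 2.45% | 1.63% |
| 250 | 2.21% | 1.47% |
| 275 | 2.01% | 1.33% |

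**Illustration in the pooled set.** This assumes that the same PT list is used for the pooled data, which the documents do not say. At n = 500 with two-sided 90% limits, counting 0 instead of 1 event gives 0.60% instead of 0.95%. Counting 1 instead of 2 gives 0.95% instead of 1.25%, so a proportion of 1% would appear to be excluded when it is not.

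**The case against.** - **Different lists for different purposes.** Section 1 defines solicited events from a diary and section 3 selects terms for an ESI; no text says that the second must contain the first. The lip terms are missing too, and the section 3 table heading speaks of laryngo-pharyngeal swellings, which is narrower than its introductory sentence. This shows that the scope could be clearer. It does not explain the gap: the list includes palatal, mouth and tongue terms, and indirect ones such as Dysphonia and Sensation of foreign body. Leaving out a direct uvula oedema term fits neither the heading nor the stated scope.
- **The investigator can flag the event.** The endpoint is defined in words, and section 12.3.3 says "The investigator must report all SAE and ESI information (initial as well as follow-up) to ALK within 24 hours". A severe uvula swelling could reach the sponsor that way, and no text says that such a report is removed because its PT is unlisted. But no text says that it enters the count either, and the only stated rule for the summary is the PT list.
- **The dictionary update.** The list is to be moved to the current MedDRA version at reporting. That does not by itself add two terms that section 1 already uses.
- **The event stays visible.** This stands. The event counts towards the primary endpoint, and TEAEs "will generally also be summarised according to severity, relationship to trial product, outcome, action taken, seriousness". It is listed, and it is a solicited event if it occurs within the 28 days.
- **Such events are rare.** This stands as well. Section 15.1 reports no severe local swelling among 265 adolescents on 12 SQ-HDM, so the missed-event figures are hypothetical. The pooled example also needs two assumed events. Neither raises the severity of the point.

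**Conclusion.** The concern holds. The section 3 list leaves out two PTs that lie within its stated scope and that the same appendix already uses, and it gives no reason. If the list is applied as written, a severe treatment-emergent uvula swelling so coded is lost from one endpoint in the 'other' tier.

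The omission itself is a plain comparison of lists and rests on no assumption. Its effect on the count depends on the PT list being the sole selection rule, on a severe uvula event occurring, and on that event being coded to one of the two PTs. One such event would lower the reported proportion from 0.4% to 0% and the 95% upper limit from 2.21% to 1.47% at n = 250. The primary and secondary endpoints are unaffected. The point is minor.

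**What to change.** Before database lock, add Enlarged uvula and Oedema uvula to the Appendix 5, section 3 list, taking it from 21 to 23 PTs, or state there why they are excluded. It would also help to say whether Lip swelling and Lip oedema are in scope. The section 3 wording on severity can stay as it is, because sections 2.4, 12.1.1 and 15.8.1 already restrict the endpoint to severe events.

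The cost is two terms in one list, handled under section 17.7 at whatever amendment class the sponsor assigns. Data collection, sample size and confidence level do not change. The timing matters because terms added after a case has been seen would look post hoc.
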